6.3. Data Management and Monitoring

Data Management: All study data, including paper CRFs, eCRFs, and the electronic database, will be managed by the trial coordinator under the supervision of the principal investigator. Participants will have the option to fill in written CRFs or eCRFs through the Research Electronic Data Capture (REDCap) platform. Study data in REDCap will be stored on a secure server managed by the Canadian College of Naturopathic Medicine and accessible only to delegated personnel. Paper CRFs will be kept at the CHI in locked cabinets. The REDCap database will be validated by two separate study staff. Full details are available in the Data Management Plan.

Data Safety and Monitoring Board (DSMB): External oversight for this trial will be provided by an independent DSMB. The primary responsibility of the DSMB is to protect the safety and welfare of participants who take part in this clinical trial and to ensure the integrity of the clinical trial. The DSMB will meet either in-person or remotely to discuss matters related to the safety of study participants (SAE/SUADR), validity and integrity of the data, enrollment rate relative to expectations, characteristics

of participants, retention of participants, adherence to the protocol (potential or real protocol deviations) and data completeness.

The DSMB will review the interim data of stage II once 100 participants are enrolled or after 2 months, whichever comes first. The DSMB may review data at other times as determined by emerging results. Based on review of the safety data, the DSMB can recommend continuation of the study without modification(s), study interruption, study termination, or modification of the trial, where applicable. Further information regarding the DSMB review process is provided in the Study DSMB Charter.

7. Adverse Events and Safety

7.1. Definitions

7.1.1. Adverse Event

According to the principles of ICH GCP, an Adverse Event (AE) is any untoward medical occurrence in a patient or clinical investigation subject administered a pharmaceutical product, a natural health product, or for whom a treatment intervention is provided, and which does not necessarily have to have a causal relationship with this treatment.

7.1.2. Serious Adverse Event

A Serious Adverse Event (SAE) is any untoward medical occurrence that at any dose: results in death, is life threatening, requires inpatient hospitalization or prolongation of existing hospitalization, results in persistent or significant disability/incapacity, or is a congenital anomaly/birth defect. The term 'life-threatening' in the definition of 'serious' refers to an event in which the patient was at risk of death at the time of the event. As such, it does not refer to an event which hypothetically might have caused death if it were more severe.

7.1.3. Adverse Drug Reaction

An adverse drug reaction is defined as a noxious and unintended response to a medicinal product related to any dose. This means that a causal relationship between a medicinal product and an adverse event is at least a reasonable possibility.

7.2. Collection and Reporting

AEs will be collected for each participant using the Common Terminology Criteria for Adverse Events (CTCAE) version 5.0. AE collection will begin following the start of the study intervention and will cease 1 week after the intervention is stopped. The exception will be AEs subject to expedited reporting to Health Canada or local REBs (defined below), in which case the AE(s) in question will be followed until completion.

Participants in both arms will be asked about adverse events each week while they are on study (day 7, 14, 21, and 28).

Adverse events will be reported to local REBs according to local requirements. Normally this would include timely reporting for events that are deemed to be unexpected, serious, and related to the study intervention. All other adverse events will be reported to the REB only in the annual renewal report. The frequency and nature of serious adverse events will be documented and reported to the DSMB.

All serious adverse drug reactions will be reported to the TPD and NNHPD. These adverse events are subject to expedited reporting. The sponsor will notify both directorates as soon as possible but no later than 7 calendar days after the sponsor becomes aware of the event for fatal or life-threatening events, and no later than 15 days after becoming aware of non-fatal/non-life threatening events. Within 8 days after having informed the NNHPD and TPD of a serious unexpected adverse drug reaction, the sponsor must submit a report as complete as possible that includes an assessment of the importance and implication of any findings. The final report should include relevant previous experience with the same or similar health products.

Medical and scientific judgment should be exercised in deciding whether expedited reporting is appropriate in other situations, such as important medical events that may not be immediately life-threatening or result in death or hospitalization but may jeopardize the participant or may require intervention to prevent one of the other outcomes listed in the definition above. These should also usually be considered serious. Examples of such events are intensive treatment in an emergency room or at home that does not require inpatient hospitalization or other severe adverse events that do not meet the criteria for being serious.

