3.1. Study Design

This study is a double-blind, placebo-controlled, phase III randomized controlled trial powered to detect meaningful differences in the overall health and symptom severity of people with COVID-19 between the treatment and control arms. Eligible participants will be randomly assigned, using a web randomization system, in a ratio of 1:1 to one of the following groups: (1) nutrient therapy with vitamin D, vitamin C, vitamin K2, and zinc or (2) placebo. Total trial duration will be 12 weeks. Nutrients or placebo will be given for a period of 21 days following enrolment and randomization. The length of the intervention period (21 days) encompasses the most common period within which recovery occurs. The median duration of time to symptom resolution is 4-8 days from testing and yet a substantial number of people (26-47%) do not return to their usual state of health within 14-21 days.³³ Available guideline recommendations support a prolonged follow up period in order to assess patients experiencing ongoing symptomatic COVID-19 (signs and symptoms for 4-12 weeks) and those with post-COVID-19 syndrome (signs and symptoms >12 weeks).³⁴

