3.4. Interventions

The interventions for this study will consist of dietary supplements for participants in the treatment arm and a placebo for those in the control arm. Three vitamins and one mineral will be included in the intervention for those in the treatment arm – vitamin D3, vitamin C, vitamin K2, and zinc. Upon enrolment and randomization, participants will be provided either dietary supplements or placebo by the study staff. Study interventions are to be started as soon as possible after enrolment and randomization and will continue for 21 days. Participants will be responsible for taking their doses and will be required to return all unused study product to the CHI or their local pharmacy to be properly destroyed. Phone calls will be made to participants at weeks 1, 2, 3, and 4 post-enrolment to check in and inquire about compliance and potential side effects.

All pill bottles will bear labels that comply with Health Canada Regulations. These labels will be in both official languages and contain the expiry date, storage conditions, lot number and the name and address of the manufacturer. An additional statement will be added to each label indicating that it is an investigational product to be used only by a qualified investigator, the trial's sponsor name and address, and protocol code. All study products will be packaged in sealed bottles. Participants will be instructed to store all products as indicated on the product label in a location that is out of reach of children and not to use if the seal is broken. Product accountability records will be maintained to track dispensation, returns and destruction of the study product, and will be maintained by the study staff at the Centre for Health Innovation (CHI). Product inventory will be stored as indicated on the label with daily temperature monitoring.

Information regarding all investigational products, including dosing, timing, absolute contraindications and rationale for use, is summarized below and in section 3.5.

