3.6. Concomitant Medications & Stopping Rules

All concomitant medications and natural health products from enrolment to end of study (3 months) will be recorded. All information will be participant-reported. Absolute contraindications are outlined in the exclusion criteria and in section 3.5. Should a participant be placed on one of these medications or be diagnosed with one of the conditions, they will stop taking the study product. Participants may also be instructed to either temporarily or permanently discontinue the intervention if the participant does not tolerate the intervention at the discretion of study doctor or treating doctor. There are no required rescue medications for this study.

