Incidence of delayed return to usual health: Measured through follow-up calls with participants after the treatment period has ended. Participants will be contacted at weeks 4, 8, and 12 to assess this. The incidence of delayed return to usual health will be defined as the presence of any symptoms related to COVID-19 at the time of these calls as reported by the participant. Those experiencing prolonged COVID-19 symptoms lasting 4-12 weeks will be classified as experiencing "ongoing symptomatic COVID-19," while those still afflicted at 12 weeks will be classified as having "post-COVID-19-syndrome."⁶²

Hospitalization: the rate and type of hospitalization, as well as the length of stay, will be collected from participant medical records where possible and will otherwise be self-reported. Information will be collected throughout the 12-week study period.

All-Cause Mortality: date of death will be collected through medical records and obituary searches when medical records are not available. Information will be collected throughout the 12-week study period.

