3.7.2. Measurement of Fever

Temperatures will be taken by the participant using a digital oral thermometer provided by the research staff. Participants will be instructed to wait 30 minutes after consumption of any fluids before taking their temperature. Consumption of fluids, especially cold,⁶³ can alter oral temperature readings by clinically meaningful amounts for up to 30 minutes,^{63,64} which, if unaddressed, may lead to measurement errors.

Table 1: Schedule of Events

	Time of Assessment										
	Screening (pre-enrolment)	Baseline (Prior to intervention)	Days 1-6	Day 7	Days 8-13	Day 14	Days 15-20	Day 21	Week 4	Week 8	Week 12
Eligibility	✓										
Informed Consent	✓										
Randomization		✓									
Medical History & Current Medications		✓									
Demographics		✓									
Study Intervention			✓	✓	✓	✓	✓	✓			
EQ-VAS			✓	✓	✓	✓	✓	✓			
Symptom Questionnaire			✓	✓	✓	✓	✓	✓			
EQ-5D-5L		✓		✓		✓		✓	✓	✓	✓
Phone Call Follow-Up • Concomitant Medications • Adverse Events • Hospitalizations • Delayed return to usual health				✓		✓		✓	✓	✓	✓

EQ-VAS: EuroQol Visual Assessment Scale; EQ-5D-5L: EuroQol 5-Dimension 5-Level. EQ-VAS and symptom questionnaires must be filled in on the appropriate days. A 3-day window will be allowed for EQ-5D-5L completion and phone call follow-up for the first 4 weeks. The window will increase to 5 days for weeks 8 and 12. Compliance to the intervention will be participant-reported and take place on day 21 or week 4.

Table 2: Outcome Assessment Methods

Objective	Assessment Method
Participant-reported health	EQ-VAS
Health Status	EQ-5D-5L
Symptom severity & duration of COVID-19 symptoms	Internally developed questionnaire
Incidence of delayed return to usual health	Call with participants
Incidence of Hospitalizations, including ER, acute care, and ICU admissions.	Data will be gathered through medical records and through calls with the participant
Length of Stay	
Incidence of Mortality	Data will be gathered through medical records or through obituary searches if medical records are not available

4. Study Conduct

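### Section 7.2 ends adverse event collection one week after the product is stopped, which conflicts with the fixed calls to day 28 for anyone stopping early, and Table 1 leaves weeks 8 and 12 unclear

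*Combined protocol and SAP*

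**What the plan says.** Section 7.2 (Collection and Reporting) ties the end of adverse event collection to each person's use of the product: "AE collection will begin following the start of the study intervention and will cease 1 week after the intervention is stopped". The one exception concerns events subject to expedited reporting, "in which case the AE(s) in question will be followed until completion". That prolongs follow-up of an event already known; it does not extend the search for new ones.

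The next paragraph of 7.2 sets fixed days: "Participants in both arms will be asked about adverse events each week while they are on study (day 7, 14, 21, and 28"). Section 3.4 (Interventions) has a matching schedule for side-effect enquiries: "Phone calls will be made to participants at weeks 1, 2, 3, and 4 post-enrolment to check in and inquire about compliance and potential side". Both schedules run on study time, and neither depends on the participant still taking capsules or drops.

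Table 1 has a single row, "Phone Call Follow-Up • Concomitant Medications • Adverse Events • Hospitalizations • Delayed return to usual health", ticked at days 7, 14 and 21 and at weeks 4, 8 and 12.

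Treatment is planned to last three weeks: "Nutrients or placebo will be given for a period of 21 days following enrolment and randomization". Section 3.6 foresees that some people will stop sooner. They may be told to "temporarily or permanently discontinue the intervention if the participant does not tolerate the intervention", and they must stop if a contraindicated medication or condition arises. Section 3.6.1 adds a pause during hospital admission. No section says whether the one-week tail in 7.2 runs from the planned or the actual end of treatment, or how a pause counts.

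**The concern.** If the cessation sentence in 7.2 governs, the length of observation depends on what the participant does after randomisation, and that may depend on the arm. Section 7.3 lists gastrointestinal effects for all four active components, and section 7.2.1 has such events recorded as adverse events because they are expected side effects. More early stopping on active is therefore plausible. Crude adverse event proportions would then rest on unequal observation time in the two arms.

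This matters mainly for the safety board. Section 4.5 lets it request unblinding because of how adverse events are distributed, and section 7.2 sends it the frequency and nature of serious events.

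A second, separate question is what staff should record at weeks 8 and 12. Table 1 can be read as calling for adverse events there; section 7.2 cannot.

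**Working it through.** **Inputs.** Planned treatment of 21 days (section 3.1); a tail of 7 days after stopping (7.2); enquiry days 7, 14, 21 and 28 (7.2); Table 1 ticks to week 12, which is 12 × 7 = day 84. The stop days below are assumed, because the documents give none. Days are counted as if the product starts at enrolment.

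**The plan's own figure.** For a completer the window ends on day 21 + 7 = 28. This reproduces the last enquiry day in 7.2, so the two rules agree for the planned course.

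**Early stopping under the literal rule.** End of window = stop day + 7; days lost against day 28 = 21 − stop day.

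| Stop day (assumed) | Window ends | Share of 28 days | Days lost | Scheduled enquiries inside window |
|---|---|---|---|---|
| 1 | 8 | 29% | 20 | 1 of 4 |
| 3 | 10 | 36% | 18 | 1 of 4 |
| 7 | 14 | 50% | 14 | 2 of 4 |
| 14 | 21 | 75% | 7 | 3 of 4 |
| 21 | 28 | 100% | 0 | 4 of 4 |

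Under the fixed-day schedule every row would end at day 28 with four enquiries.

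**Effect on mean observation time.** Mean = (1 − p) × 28 + p × (stop day + 7), where p is the share stopping early. Take p = 15% on active and 5% on placebo; both are assumptions with no source in the documents.

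- Stop on day 3: active 0.85 × 28 + 0.15 × 10 = 25.3 days; placebo 0.95 × 28 + 0.05 × 10 = 27.1 days. Ratio 0.93, about 7% less on active.
- Stop on day 10: active 0.85 × 28 + 0.15 × 17 = 26.35; placebo 0.95 × 28 + 0.05 × 17 = 27.45. About 4% less.
- Stop on day 14: active 0.85 × 28 + 0.15 × 21 = 26.95; placebo 0.95 × 28 + 0.05 × 21 = 27.65. About 2.5% less.
- Equal shares and timing in both arms: no difference.

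**Table 1.** Taken at face value, the row extends adverse event enquiry by 84 − 28 = 56 days beyond the 7.2 window, even for completers. But the row is composite. Delayed return to usual health shares all its ticks, including days 7, 14 and 21, whereas section 3.7 says of that outcome: "Participants will be contacted at weeks 4, 8, and 12 to assess this". So the ticks cannot all apply to every item, and those at weeks 8 and 12 may not be meant for adverse events. No footnote says which.

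**The case against.** The strongest reply is that the plan, read as a whole, already covers early stoppers. The two rules coincide for the planned course, and the fixed enquiries in 7.2 and 3.4 apply to both arms whether or not the product is still taken. If staff make every call through week 4 and record what they hear, nobody is cut short. This stands as a possible reading. It does not settle the matter, because the cessation sentence tells staff otherwise and nothing says which rule prevails.

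A reader might go further and infer that people who stop for intolerance are in fact followed for the shortest time, and that the safety comparison is biased in favour of the active arm. The documents do not support that:

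- The shorter window follows only under the literal reading, and it would apply to anyone who stops early, including for a new contraindication.
- The event that prompts stopping would normally be recorded already, and another week off product is covered.
- More stopping on active is assumed. Section 7.2.1 notes that gastrointestinal disturbances are also COVID-19 symptoms, so they will occur on placebo too.
- Section 6.2.2 specifies no between-arm test of adverse events.

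Nor should Table 1 be read as firmly setting a week-12 end point, given its composite row.

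Finally, serious events in weeks 5 to 12 are not simply lost. Death and inpatient admission meet the serious definition in 7.1.2, and both are collected as outcomes over the full 12 weeks (section 3.7).

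**Conclusion.** The inconsistency is real and modest. The one-week tail and the day-28 schedule agree for completers and conflict for anyone stopping before day 21. Table 1 adds an unresolved question about weeks 8 and 12 for everyone.

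Under the literal rule an early stopper loses 21 minus the stop day, in days of observation. Whether this creates a difference between arms depends on stopping rates that the documents do not give. The range of about 2.5% to 7% less mean observation on active rests on the assumed 15% against 5% and on stop days 14 to 3; it is an illustration, not an estimate.

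What could be missed is narrow: adverse events that begin or recur more than a week after stopping, and serious events that involve neither death nor admission. The serious-event tally could also disagree with the 12-week hospitalisation and death outcomes, because the same late admission would count as an outcome but fall outside adverse event collection.

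**What to change.** In section 7.2, replace the cessation rule with one window for every randomised participant: from first dose through the week-4 call, regardless of when or why the product was stopped or paused. Keep the expedited-reporting exception. Tying the end to the call also avoids a mismatch of clocks, since section 3.7.1 counts calls from enrolment whereas adverse event collection starts with the product.

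In Table 1, split the call row or add a footnote saying which items apply at weeks 8 and 12. Record serious events at those two calls, so that the serious-event tally matches the 12-week hospitalisation and death outcomes. Then make 7.2 and Table 1 say the same.

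The calls are already scheduled and no treatment rule changes. The cost is protocol wording and a few more event forms. The window will still vary slightly with the 3-day allowance for the week-4 call and with any delay in the first dose, but it will no longer depend on stopping.

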7.2.1. Exceptions

AEs will not be recorded if the participant experiences classic or other symptoms of COVID-19 that are not deemed serious as defined above. These include fever, new or worsening cough, shortness of breath/difficulty breathing, fatigue, myalgia/arthralgia, sore throat, sputum production, dysphagia (difficulty swallowing), new olfactory or taste disorders, pneumonia, rhinorrhea (runny nose), chills/shakes, or nasal congestion. Such events are expected in a population who are COVID-19 positive and are not deemed deviations from the normal course of the disease. GI disturbances (e.g., nausea, vomiting, diarrhea, upset stomach) are also considered symptoms of COVID-19 but will be reported as AEs as they are expected side effects of the interventions being studied.

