2.1.2. Secondary Objectives

Secondary objectives include:

1. Effect of COVID-19 on the health status of participants
2. Symptom severity of COVID-19 symptoms, including: fever, cough, shortness of breath, fatigue, headache, myalgia/arthralgia (body aches), nausea, vomiting, diarrhea, shakes/chills, congestion, and loss of taste and smell
3. Total symptom duration
4. Incidence of delayed return to usual health
5. Frequency of hospitalizations, including: ER visits, acute care admissions, and ICU admissions
6. Hospital length of stay
7. All-cause mortality

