3.7. Outcome Measurements & Timeline

Participant-Reported Overall Health: measured using the EuroQol visual analogue scale (EQ-VAS).⁵⁹ The EQ-VAS records the respondent’s overall current health on a vertical scale between 0 and 100, where the end points are labelled “the best health you can imagine” (i.e., a score of 100) and “the worst health you

can imagine" (i.e., a score of 0). The EQ-VAS will be filled out each day while on the intervention (21 days total).

Health Status: Measured by combining one level from each of the five dimensions of the EuroQol 5-dimension 5-level (EQ-5D-5L) questionnaire⁵⁹ (mobility, self-care, usual activities, pain/discomfort, and anxiety/depression) to form a unique health state. Each dimension is divided into five levels of perceived problems: 1 – no problem, 2 – slight problems, 3 – moderate problems, 4 – severe problems, and 5 – unable to perform/extreme problems. The EQ-5D-5L questionnaire will be filled in at baseline (i.e., before starting the intervention) and weeks 1, 2, 3, 4, 8, and 12.

Symptom Severity & Duration: Measured using an internally-developed questionnaire specific for the most common COVID-19 symptoms, which include: fever, cough, shortness of breath, fatigue, headache, myalgia/arthralgia (body aches), nausea, vomiting, diarrhea, chills, altered taste, altered smell, and nasal congestion.^{11,60} Each symptom will be rated based on severity with a 4 point scale (0-3): 0-none, 1-slight, 2-moderate, and 3-severe. Participants will fill in this questionnaire each day while receiving treatment (i.e., for 21 days).

The questionnaire is largely based on recommendations from the US Food and Drug Administration (FDA) guidance document for investigators conducting community clinical trials for COVID-19 prevention or treatment.⁶¹ The symptoms were selected based on the most commonly reported COVID-19 symptoms in both the hospital and community setting.^{11,60} Some of the same symptoms are also included in the questionnaire being used in a study of vitamin C and zinc (COVIDAtz) at the Cleveland clinic, potentially allowing for comparison of results.²⁹

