6.2.1.2. Symptom Severity & Duration

Symptom severity will be conducted using an area under the curve approach comparing the difference in total symptom scores over the 21-day intervention period between both arms. This gives a score range of 0-882 for each participant (i.e., 0-42 each day for 21 days). As a secondary analysis, we will compare the severity of each symptom individually using the same area under the curve approach. Scores for each symptom will range from 0-63 (i.e., 0-3 each day for 21 days). The incidence of severe symptoms (i.e., reporting a “3” for any symptom) will also be compared between arms throughout the intervention period.

The symptom duration analysis will compare the median time to symptom resolution from the start of the intervention period (or the first onset of symptoms if no symptoms were present at the start of the intervention period) up to the end of the intervention period (day 21) between both arms. Symptom resolution will be defined as a zero in all categories with no relapses.

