7.3. Expected Adverse Events

According to the Health Canada approved product monographs, reports in the literature and clinical experience, the expected adverse events associated with each component of the intervention are listed below. Any other symptoms experienced by a participant (provided they are not COVID-19 related) would be considered unexpected.

Vitamin D: nausea/vomiting, constipation, upset stomach

Vitamin C: GI upset (nausea, vomiting, appetite loss, stomach discomfort, diarrhea, gastric ulcer), headache, hyperoxaluria, apparent decrease in uric acid levels

Vitamin K: GI upset (nausea, vomiting, appetite loss, stomach discomfort, diarrhea, gastric ulcer)

Zinc: nausea/vomiting, abdominal pain, diarrhea

There are no expected serious adverse events for this population.

8. Privacy and Confidentiality

Participant personal health information (PHI) will be kept confidential unless release is required by law. Representatives of the OHSN-REB, OHRI, CCNM REB, NNHPD, or TPD may review original medical records under the supervision of [name] staff for audit purposes.

Participants will not be identified in any publications or presentations resulting from this study, unless permission is given by the participant. All paper case report forms will be kept in locked cabinets in a locked office and all databases will be password protected on a secure server. These documents and relevant source documents will be kept for a period of 25 years as required by Health Canada. Case report forms will be shredded, and databases will be erased at the end of this retention period.

9. Dissemination and Knowledge Transfer

The work done in this study will be disseminated in the form of scientific presentations to complementary, integrative and traditional medical conferences within Canada and internationally. Presentations will be accompanied by published abstracts. The principal mechanism for knowledge transfer will be publication and will include the use of social media as well as press. We will target the most reputable clinical journal for publication due to the potential impact of this investigation.

10. Relevance and Impact

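### Section 7.2.1 exempts five non-serious events, pneumonia among them, from AE recording although none is a named item on the daily questionnaire, so most of them have no symptom-level record in either arm

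*Combined protocol and SAP*

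**What the plan says.** Section 7.2.1 sets the exemption: "AEs will not be recorded if the participant experiences classic or other symptoms of COVID-19 that are not deemed serious as defined above". The list that follows begins with fever, cough, breathing difficulty, fatigue and muscle or joint pain, and continues with "sore throat, sputum production, dysphagia (difficulty swallowing), new olfactory or taste disorders, pneumonia, rhinorrhea (runny nose), chills/shakes, or nasal congestion". GI disturbances are brought back in; they "will be reported as AEs as they are expected side effects of the interventions being studied".

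The instrument that grades symptoms is the daily questionnaire of section 3.7, completed for 21 days and scored 0-3 per symptom. It is described as covering "fever, cough, shortness of breath, fatigue, headache, myalgia/arthralgia (body aches), nausea, vomiting, diarrhea, chills, altered taste, altered smell, and nasal congestion". The matching secondary objective in section 2.1.2 names the same symptoms: "fever, cough, shortness of breath, fatigue, headache, myalgia/arthralgia (body aches), nausea, vomiting, diarrhea, shakes/chills, congestion, and loss of taste and smell". Section 6.2.1.2 gives the total score as 0-42 per day and 0-882 over 21 days, and plans a comparison of each symptom separately.

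Section 7.2 has study staff ask both arms about AEs on days 7, 14, 21 and 28. Section 7.3 lists expected effects by ingredient; the vitamin C entry includes "diarrhea, gastric ulcer), headache, hyperoxaluria, apparent decrease in uric acid levels".

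**The concern.** Leaving disease symptoms out of the AE record is common in a trial of sick participants. It loses little if another instrument collects the same events in both arms. Here the exempt list and the questionnaire list do not match: five exempt events are not named on the questionnaire.

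What is at stake is the randomised, blinded comparison, which is the only thing in this design that separates an effect of the product from the course of COVID-19. An event assigned to the disease before it is recorded cannot be compared by arm. This matters most for pneumonia, which is a diagnosis marking worsening disease rather than a mild symptom. Section 4.5 gives the distribution of AEs as an example of why the DSMB might ask for unblinding, and exempt events never enter that distribution. The words 'or other' also leave the class open, so what is exempt can vary with whoever makes the call.

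**Working it through.** **Step 1. Match the two lists.** Section 7.2.1 has 13 entries, or 14 if smell and taste are counted separately as in section 3.7.

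| Exempt under 7.2.1 | Named on the questionnaire (3.7)? |
|---|---|
| fever, cough, shortness of breath, fatigue, myalgia/arthralgia, smell, taste, chills, nasal congestion (9) | yes |
| pneumonia, dysphagia, sore throat, sputum production, rhinorrhea (5) | no |

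Check: 9 + 5 = 14. The four questionnaire items not named in 7.2.1's exempt list are headache, nausea, vomiting and diarrhea (9 + 4 = 13). The last three are explicitly kept as AEs.

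**Step 2. Test whether the questionnaire list is complete.** The plan's own score range does not reproduce from the named items.

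- Named items: 13 × 3 = 39 per day; 39 × 21 = 819 over 21 days.
- Stated: 42 per day and 882 over 21 days.
- Items implied: 42 / 3 = 14, and 882 / (3 × 21) = 882 / 63 = 14.

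So either one scored item is unnamed or the range is wrong. The range allows no more than one extra item.

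**Step 3. Bound the number of uncollected events.**

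- Range wrong, or 14th item not one of the five: 5 uncollected.
- 14th item is one of the five: 5 − 1 = 4.
- As above, and nasal congestion is also read to cover runny nose: 4 − 1 = 3. Section 7.2.1 lists the two separately, so this is the generous reading.

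**Step 4. Look for any other record of the non-serious events.**

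| Source | What it records |
|---|---|
| SAE definition and important medical events (7.1.2, 7.2) | serious cases, and by judgement those treated intensively in an ER or at home |
| ER visits and admissions (6.2.1.4) | the visit or admission, compared between arms |
| Calls at weeks 4, 8 and 12 (3.7) | whether any COVID-19 symptom is present, not which one |
| EQ-VAS, EQ-5D-5L (3.7) | overall health, not events |
| Concomitant medications (3.6) | at most an indirect trace |

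None of these gives a symptom-level record of the five events when they are non-serious. For pneumonia, what is left uncovered is a non-serious case managed without an ER visit.

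**Step 5. Headache.** It is not named in 7.2.1, but section 3.7 treats it as a common COVID-19 symptom, so the words 'or other' can be read to exempt it. Section 7.3 lists it as expected with vitamin C, which is the ground on which 7.2.1 keeps GI events. The text does not settle which applies.

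**The case against.** The strongest reply is that the exemption is a legitimate design choice and that much of what it removes is seen elsewhere. Cough, breathlessness, fever and fatigue, which would accompany most pneumonias, are graded daily and compared one by one. Severe cases reach the SAE or ER record. No efficacy outcome or error rate changes. All of this stands, and it limits the point to the events in Step 3. It does not remove the point: component symptom scores do not identify a pneumonia diagnosis, and an ER comparison misses cases that never went there.

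A reader might infer four stronger things that the documents do not support.

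- *That all five events are certainly uncollected.* The questionnaire itself is not in the documents, its list is introduced as non-exhaustive, and the 0-42 range points to one more item.
- *That any pneumonia treated at home goes unrecorded.* Section 7.2 says events treated intensively at home should usually count as serious, so some would be recorded.
- *That exempting dysphagia hides harm from the number of capsules taken.* Section 3.5 gives a matching placebo capsule for each capsule product, so a swallowing problem caused by capsule burden would be expected in both arms and would not show as a difference. Section 7.3 lists dysphagia for no ingredient.
- *That the exemption should lapse for all symptoms when the questionnaire stops at day 21.* Section 3.1 reports that 26-47% had not regained usual health by 14-21 days. Applied to 200 enrolled as a rough illustration, that is 0.26 × 200 = 52 to 0.47 × 200 = 94 people whose lingering symptoms could become AEs after study product has ended. That is a debatable trade, not a clear improvement.

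Headache is likewise no gap in measurement on days 1-21, since it is a graded item compared between arms. What needs attention is its status as an AE.

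**Conclusion.** The concern holds in limited form. Between three and five of the listed exempt events have no symptom-level record when non-serious: at least four if rhinorrhea is taken as distinct from nasal congestion, three if not. The main loss is the between-arm comparison of non-serious pneumonia managed without an ER visit. The lower bounds assume that each questionnaire item is scored 0-3, as section 3.7 says, and that the stated range is right, so that at most one item is unnamed. Naming pneumonia as the main gap assumes that the unnamed item is not pneumonia, which as a diagnosis would be an odd entry on a 0-3 symptom scale. The documents give no expected frequency for these events, so the number of cases lost cannot be estimated. The change is worth making because it is cheap and data not collected during the trial cannot be reliably recovered afterwards. The gap does not undermine the efficacy analysis or the capture of serious harm.

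**What to change.** In section 7.2.1:

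1. Limit the exception to symptoms that are items on the daily questionnaire, and delete 'or other'.
2. Record pneumonia, and any other listed event that is not on the questionnaire, as CTCAE-graded AEs in both arms at the existing day 7, 14, 21 and 28 calls.
3. State that headache is kept as an AE, on the same reasoning as GI events.

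In sections 2.1.2, 3.7 and 6.2.1.2, reconcile the 13 named symptoms with the 0-42 and 0-882 ranges: name the 14th item, or correct the ranges to 0-39 and 0-819. This also settles which exempt events are on the form.

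The cost is a paragraph of wording and a few more AE lines, with no new visit or call and no change to sample size or efficacy analysis. Some of the added events will be COVID-19 itself. Randomisation balances that background between arms in expectation, so it adds noise to the comparison rather than bias.
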